#### 4.4.1.1.5 Number of Days of Occurrence

Number of days of occurrence during the period considered will be derived from the daily intensities computed as described in [Section 4.4.1.1.1](#). It corresponds to the number of days with daily intensities of Grade 1, Grade 2, or Grade 3. The number of days of occurrence during the solicited period with a specified intensity may also be derived. For subjects who received 2 doses, the worst case-scenario will be used for the post any dose summary (i.e., the larger number of days will be used if present for both doses, or the available number of days will be used if present for either dose).

#### 4.4.1.1.6 Overall Number of Days of Occurrence

If a reaction is ongoing at the end of the solicited period, then the overall number of days of occurrence will be derived from the daily intensities and the stop date of the reaction after the end of the solicited period. The overall number of days of occurrence will be:

$$(\text{stop date} - \text{last vaccination date}) + (\text{number of days of occurrence within the solicited period}) - \text{length of the solicited period} + 1$$

If the stop date is missing or incomplete (contains MD), the overall number of days of occurrence will be considered as Missing. For subjects who received 2 doses, the worst-case scenario will be used for the post-any dose summary (i.e., the larger number of days will be used if present for both doses, or the available number of days will be used if present for either dose).

#### 4.4.1.1.7 Ongoing

Ongoing will be derived from the last daily intensity of the solicited period computed as described in [Section 4.4.1.1.1](#) and the maximum intensity during the ongoing period. The Investigator's ongoing flag is not used because the measurement would determine the ongoing status of the reaction.

If the last daily intensity of the solicited period is at least Grade 1 and the maximum intensity in the ongoing period is also at least Grade 1, then the reaction is considered ongoing. In all other cases, the reaction will not be considered as ongoing.

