## 4.4 Derived Endpoints: Calculation and Derivation Methods

### 4.4.1 Safety

#### 4.4.1.1 Solicited Reactions

##### 4.4.1.1.1 Daily Intensity

All daily records for solicited reactions will be derived into daily intensity according to the following classification: None, Grade 1, Grade 2, Grade 3, or Missing.

For the derivation of daily intensities, the following sequential steps will be applied:

- 1) For solicited reactions (except fever/pyrexia) for which an Investigator records their presence as “No” and for which all daily records are missing, all daily intensities will be derived as None
- 2) For a temperature with partially missing data (MD) after the decimal point, the data will be analyzed by replacing “MD” with zero. For example, a “39.MD°C” daily temperature will be considered as “39.0°C” in the analysis
- 3) For non-measurable solicited reactions, daily intensities will correspond to daily records reported in the clinical database. For measurable solicited reactions, the daily measurements reported in the clinical database will be converted based upon the intensity scales defined in the protocol; this assumes a reaction that is too large to measure (non-measurable, “NM”) is Grade 3

Note: The maximum intensity during the ongoing period will be derived from the record of the maximum intensity/measurement after the end of the solicited period following the rule described above.

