### **5.3.1.5 Start Date and Stop Date**

No replacement of missing dates will be performed.

For instance:

- If the onset of an AE cannot be calculated due to a missing start date, then the onset will be considered as missing
- If the stop date of an unsolicited AE is missing, then the duration of that AE will be considered as missing
- If the stop date of a solicited reaction continuing after the solicited period is missing or incomplete, then the number of days of occurrence of that solicited event will be considered as missing

All missing and partially missing dates will be listed where appropriate.

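### When only one of the two intensities that decide ongoing status is recorded, and it is positive, the SAP classes the reaction as not ongoing even if the stop date or the Investigator's flag shows that it continued

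*SAP*

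**What the plan says.** SAP 4.4.1.1.7 sets a two-part condition, which opens "If the last daily intensity of the solicited period is at least Grade 1 and the maximum intensity in the ongoing period is also" (the second part has the same threshold as the first). A reaction that meets both parts counts as ongoing. Everything else is covered by one sentence: "In all other cases, the reaction will not be considered as ongoing". The Investigator's "ongoing flag is not used because the measurement would determine the ongoing status of the reaction".

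Three neighbouring rules matter.

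- SAP 4.4.1.1.1 lists the possible daily intensities as "None, Grade 1, Grade 2, Grade 3, or Missing". The later component comes from one further record: "The maximum intensity during the ongoing period will be derived from the record of the maximum intensity/measurement after the end of the solicited period". It follows the same derivation rule, so it too can be Missing.
- SAP 4.4.1.1.5 defines the in-period count: "It corresponds to the number of days with daily intensities of Grade 1, Grade 2, or Grade 3". Missing days are not counted.
- SAP 4.4.1.1.6 gives the stop-date formula for the overall number of days, under the condition "If a reaction is ongoing at the end of the solicited period". If the stop date is missing or incomplete, the overall number is Missing. SAP 5.3.1.5 gives the same outcome, opening "If the stop date of a solicited reaction continuing after the solicited period is missing or incomplete".

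**The concern.** SAP 4.4.1.1.7 has no branch for a Missing component, so a blank has the same effect as a recorded None. That is reasonable when nothing else points to continuation. It is not reasonable when the other component is positive and a stop date after Day 7, or the Investigator's flag, shows that the reaction went on. The reason given for setting the flag aside is that the measurement settles the matter, and that reason fails when the measurement is absent.

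Because 4.4.1.1.6 applies only to ongoing reactions, the recorded stop date is then not used, and the Missing outcome in 4.4.1.1.6 and 5.3.1.5 is not reached. The reaction is left with its in-period count. In these patterns the error can only shorten the duration, and it falls on reactions that outlast the solicited period. Those are the reactions a reader would look at when judging how long reactions persist at either dose.

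**Working it through.** **Inputs.** The solicited period is Day 0 to Day 7 (SAP 4.1.2), which is 8 daily records. The overall number of days (SAP 4.4.1.1.6) is (stop date − last vaccination date) + in-period days − length of solicited period + 1. Stop dates below are in days since the last vaccination. The cases are illustrations, since the documents give no data on this.

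**Check of the formula.** Grade 1 on all of Days 0 to 7 with a stop on Day 10 gives 10 + 8 − 8 + 1 = 11. This equals the inclusive count from Day 0 to Day 10. A period length of 7 would give 12, so 8 is the right length.

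**Classification.** Each component can be None, Grade 1 or higher, or Missing, which makes 3 × 3 = 9 combinations. Only one is ongoing (both positive). Five contain a Missing component, and all five come out as not ongoing. In two of the five the other component is positive: Day 7 positive with the later record Missing, and Day 7 Missing with the later record positive. This point concerns those two patterns.

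**Worked cases.** Days not listed are None. For a not-ongoing reaction, the current-rule column shows the in-period count.

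| Daily record | Later maximum | Stop date | Current rule | If treated as ongoing |
|---|---|---|---|---|
| Grade 1, Days 0–7 | Grade 1 | Day 20 | 21 | 20 + 8 − 8 + 1 = 21 |
| Grade 1, Days 0–7 | Missing | Day 20 | 8 | 21 |
| Grade 1, Days 5–7 | Missing | Day 20 | 3 | 20 + 3 − 8 + 1 = 16 |
| Grade 2, Days 3–6; Day 7 Missing | Grade 2 | Day 12 | 4 | 12 + 4 − 8 + 1 = 9 |
| Grade 1, Days 0–6; Day 7 Missing | Grade 1 | Day 20 | 7 | 20 + 7 − 8 + 1 = 20 |
| Grade 1, Days 0–7 | Grade 1 | none | Missing | Missing |
| Grade 1, Days 0–7; flag set | Missing | none | 8 | Missing |

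The first two rows differ only in whether the later intensity was filled in: 21 days against 8. In the last two rows neither case has a stop date. The one that also lacks the later intensity gets a definite 8 days, while the better documented one gets Missing. An affected reaction cannot exceed 8 days, or 7 if Day 7 is the blank.

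In the fourth row the formula gives 9, while the calendar span from Day 3 to Day 12 is 10. The unrecorded Day 7 is not counted, which is consistent with not replacing missing data.

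**The case against.** Several counter-arguments are sound, and they limit the point.

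- **Endpoint.** A reader might infer that the listed endpoint, number of days of occurrence, is biased. It is not. SAP 4.3.1.2 restricts it to Day 0 to Day 7, and 4.4.1.1.5 derives it from daily intensities without using ongoing status. The overall number of days is a separate derived quantity. It is not in the endpoint list, and whether it is tabulated depends on the separate tables file named in SAP section 6.
- **Contradiction with 5.3.1.5.** A reader might see one. But 5.3.1.5 handles reactions already known to be continuing, and 4.4.1.1.7 decides which those are. The later rule is bypassed, not contradicted.
- **Worst-case wording.** In 4.4.1.1.4 to 4.4.1.1.6 it says only how two doses are combined in the post-any-dose summary. It is not a missing-data principle that the ongoing rule breaks.
- **Bias between arms.** The rule is the same in both groups, safety assessors are blinded (Protocol 6.4) and the analysis is descriptive. Nothing in the documents shows a differential effect.
- **Blanks are often right.** A reaction that ended on Day 7 may well have no later record, so not every blank is lost information. Parents are interviewed about the diary, unclear entries are followed up and omissions are checked for (Protocol 9.3.1.3, 11.1, 11.2, 13.2).
- **Preferring measurement to a flag** is a declared and defensible choice when the measurement exists.

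What remains is the case where one component is positive, the other is blank, and recorded evidence of continuation is ignored. Reading the last daily intensity as the last non-missing one would settle the pattern with Day 7 blank, but not the pattern with the later record blank. The text does not say that this is meant.

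**Conclusion.** The point holds in a narrow form. For the two mixed patterns, the literal rule overrides a stop date after Day 7 and the Investigator's flag. In the worked cases with a stop date, it replaces 9 to 21 days by 3 to 8. Where the flag is set and no stop date exists, it replaces Missing by a number.

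This rests on two readings. First, Missing falls under the catch-all sentence, since no other branch exists. Second, a not-ongoing reaction keeps its in-period count. The SAP does not state the second, but it defines no other value.

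The effect is confined to ongoing status and the overall number of days. Occurrence, maximum intensity in the solicited period, the Day 0 to 7 count and the primary fever endpoint do not change. The documents do not say how often such blanks arise. The number of children is probably small, so the total effect cannot be calculated. This is a minor correction, worth making because it costs little.

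**What to change.** Keep the current rule in SAP 4.4.1.1.7 whenever both components are recorded, and add a branch for the two mixed patterns only:

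- (a) Day 7 Missing and the later maximum Grade 1 or higher: ongoing.
- (b) Day 7 Grade 1 or higher and the later maximum Missing: ongoing if a stop date after Day 7 or the Investigator's ongoing flag is recorded; otherwise not ongoing.

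Then apply 4.4.1.1.6 as it stands, with the overall number of days Missing when the stop date is missing or incomplete. Do not carry daily intensities forward, because SAP 5.3.1 rules out replacing missing safety data. Leave reactions with a recorded None on Day 7 unchanged. A wider rule that set every unresolved blank to Missing would discard reactions that had visibly ended, for example Grade 1 on Day 1 and None on Days 2 to 7 with nothing recorded afterwards.

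The cost is a few lines of SAP text and a small programming change. The SAP already refers to the later intensity record, the stop date and the flag, so no new data are needed. A few overall durations will become longer or Missing.

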#### 4.4.1.2 Unsolicited Non-serious AEs

##### 4.4.1.2.1 Intensity

Intensity for unsolicited non-serious AEs will be derived according to the following classification: None, Grade 1, Grade 2, Grade 3, or Missing.

If the unsolicited non-serious AE is measurable and its MedDRA PT is part of the list of solicited reactions, then the measurement will be derived based upon and following the same rule as the intensity scales defined in the protocol for that measurable injection site or systemic reaction. Intensity for the other unsolicited non-serious AEs will correspond to the value reported in the eCRF.

The maximum intensity will correspond to the highest intensity for a unique term. **Last Vaccination**

The last vaccination before an unsolicited non-serious AE is derived from the visit numbers provided in the clinical database and will be calculated as follows:

- If an unsolicited non-serious AE has a non-missing visit number, the visit number will be used to determine the last vaccination before the unsolicited non-serious AE
- If the visit number is missing, then the start date of the unsolicited non-serious AE will be used to determine the last vaccination before the unsolicited non-serious AE

##### 4.4.1.2.3 Time of Onset

Time of onset will be derived from the start date of the unsolicited non-serious AE provided in the clinical database and the date of last vaccination:

start date of the unsolicited non-serious AE - date of previous vaccination

The time of onset will be considered as missing only if 1 or both of the dates are missing or partially missing.

Adverse events with a missing time of onset will be considered to have occurred just after the vaccination indicated by the visit number and will be included in tables. For subjects who received 2 doses, the worst-case scenario will be used for the post-any dose summary (i.e., the smaller time of onset [latency] period will be used if present for both doses or the available time of onset [latency] period will be used if present for either dose).

Note: Unsolicited non-serious AEs that occurred before vaccination (negative time of onset) will not be included in the analysis, but will be listed separately.

##### 4.4.1.2.4 Duration

Duration will be derived from the start and stop dates of the unsolicited non-serious AE provided in the clinical database:

stop date of unsolicited non-serious AE - start date of unsolicited non-serious AE + 1.

The duration will be considered as missing only if 1 or both of the start and stop dates of the unsolicited non-serious AE is missing or partially missing. For subjects who received 2 doses, the worst-case scenario will be used for the post-any dose summary (i.e., the longer duration will be used if present for both doses or the available duration will be used if present for either dose).

#### 4.4.1.3 Serious Adverse Events

##### 4.4.1.3.1 Last Vaccination

The last vaccination before an SAE will be derived from the last visit number provided in the clinical database and will be calculated as follows:

- If an SAE has a non-missing visit number, the visit number will be used to determine the last vaccination before the SAE
- If the visit number is missing, then the start date of the SAE will be used to determine the last vaccination before the SAE

##### 4.4.1.3.2 Time of Onset

Time of onset will be computed using the same methodology as for unsolicited non-serious AEs described in [Section 4.4.1.2.3](#).

##### 4.4.1.3.3 Duration

Duration will be computed using the same methodology as for unsolicited non-serious AEs described in [Section 4.4.1.2.4](#).

#### 4.4.2 Immunogenicity

##### 4.4.2.1 Computed Values for Analysis

To appropriately manage extreme values ( $< \text{LLOQ}$  and  $\geq \text{ULOQ}$  [upper limit of quantification]) for analysis purposes, the following computational rules will be applied to the values provided in the clinical database for each blood sample drawn, as appropriate:

- If a value is  $< \text{LLOQ}$ , then use the computed value  $\text{LLOQ}/2$
- If a value is  $\geq \text{LLOQ}$  and  $< \text{ULOQ}$ , then use the value
- If a value is  $\geq \text{ULOQ}$ , then use the value  $\text{ULOQ}$

##### 4.4.2.2 Seroprotection

If the computed value is  $\geq 40$  (1/dil) at pre-vaccination and at post-final vaccination, then the derived seroprotection indicator will be “Yes” for that test, otherwise seroprotection will be “No”.

Note: If the computed value is missing, seroprotection will be missing ██████████

#### 4.4.2.4 Seroconversion

If a pre-vaccination titer is  $< 10$  (1/dil) and a post-final vaccination titer is  $\geq 40$  (1/dil), or a pre-vaccination titer is  $\geq 10$  (1/dil) and there is a  $\geq 4$ -fold increase in post-final vaccination titer, then the derived seroconversion indicator will be “Yes” for that test, otherwise seroconversion will be set to “No”.

#### 4.4.3 Efficacy

Not applicable.

#### 4.4.4 Derived Other Variables

##### 4.4.4.1 Age for Demographics

To calculate age at enrollment, the following algorithm will be used:

- The difference in years will be calculated by subtracting the year of birth from the year of the enrollment visit; this difference will be multiplied by 12 to get the difference in months
- The month of birth will be subtracted from the month of the enrollment visit
- The values calculated above will be added to obtain a provisional age in months
- It will be determined when the day of the enrollment visit (e.g., the 31st day of the month) occurred relative to the day of birth (e.g., the 28th day of the month). The final age in months will be determined as follows:

- a) If the day of the enrollment visit  $\geq$  day of birth, then the sum calculated above will be considered the final age in months; otherwise,
- b) If the day of the enrollment visit  $<$  day of birth, then the sum calculated above will be reduced by 1 month to obtain the final age in months

#### 4.4.4.2 Duration of a Subject’s Participation in the Trial

The duration of a subject’s participation in the study will be computed as follows:

maximum date (of visit, of termination form) - date of Visit 1 +1.

#### 4.4.4.3 Duration of the Study

The duration of the study will be computed as follows:

maximum date (of visit, of termination form) of all subjects – minimum date of Visit 1 for all subjects +1.

## 5 Statistical Methods and Determination of Sample Size

The statistical analyses of the data will be performed under the responsibility of the Sanofi Pasteur Biostatistics and Programming platform using SAS® Version 9.2 software or later.

The results of the statistical analysis will be available in the final clinical study report (CSR).

The distribution of the subjects enrolled into the study will be summarized by investigative site and enrollment group. A description of the populations will be presented. The number of subjects enrolled, age at enrollment (mean, median, minimum, and maximum), sex, and ethnic origin and racial origin will be summarized, as well as the number and description of protocol violations will be presented.

Continuous variables will be presented by summary statistics (e.g., mean and standard deviation [SD]) for the non-immunogenicity endpoints; geometric means (GMs) and their confidence intervals (CIs) for the immunogenicity endpoints), and the categorical variables will be presented by frequency distributions (frequency counts, percentages, and their CIs for the main endpoints).

For descriptive purposes, the following statistics will be presented:

**Table 5.1: Descriptive Statistics Produced**

Baseline characteristics and follow-up description	Categorical data	Number of subjects Percentage of subjects
	Continuous data	Mean, SD, quartiles, minimum, and maximum
Clinical safety results	Categorical data	Solicited: Number and percentage (95% CIs) of subjects Unsolicited: Number and percentage (95% CIs) of subjects, and number of events

	Continuous data	Mean, SD, quartiles, minimum, and maximum
Immunogenicity results	Categorical data (seroprotection, seroconversion, cutoff)	Number and percentage of subjects, and 95% CI
	Continuous data (titer data and fold-rise)	log 10 : Mean and SD Anti-log 10 (work on log 10 distribution, and anti-log 10 applied): GM, 95% CI of the GM, quartiles, minimum, and maximum. Graphical representation by Reverse Cumulative Distribution Curve

CI: confidence interval; GM: geometric mean; SD: standard deviation

The CI for the single proportion will be calculated using the exact binomial method (Clopper-Pearson method, quoted by Newcombe (3), i.e., using the inverse of the beta integral in SAS®).

For immunogenicity results, assuming that log10 transformation of the titers follows a normal distribution, at first, the mean and the 95% CI will be calculated on log10 (titers/data) using the usual calculation for normal distribution (using Student's t distribution with n-1 degree of freedom), then antilog transformations will be applied to the results of calculations, in order to provide GMs and their 95% CI.

Rounding rules on descriptive statistics edited will follow the Sanofi Pasteur standard working instruction ("Conventions for the Presentation of Descriptive Statistics"). To present percentages (and 95% CIs of percentages), 1 digit after the decimal place will be used unless indicated otherwise.

## 5.1 Statistical Methods

### 5.1.1 Hypotheses and Statistical Methods for Primary Objective

For descriptive purposes, the statistics presented on Table 5.1 will be produced.

The Safety Analysis Set (SafAS) population will be used to establish non-inferiority for the primary objective.

#### 5.1.1.1 Hypotheses

During the 7 days after either vaccination (Dose 1 and Dose 2 combined), the 0.5-mL dose of Fluzone Quadrivalent vaccine will be non-inferior to the 0.25-mL dose of Fluzone Quadrivalent vaccine in terms of fever reaction (temperature  $\geq 100.4^{\circ}\text{F}$  [ $38.0^{\circ}\text{C}$ ]) in subjects 6 to < 36 months of age. The null and alternative hypotheses are:

$$H_0: P_{0.5\text{mL}} - P_{0.25\text{mL}} \geq 5\%$$

$$H_A: P_{0.5\text{mL}} - P_{0.25\text{mL}} < 5\%$$

Where:

$P_{0.25\text{mL}}$  = percentage of subjects with fever reaction (temperature  $\geq 100.4^{\circ}\text{F}$  [ $38.0^{\circ}\text{C}$ ]) after vaccination with the first dose and/or the second dose of 0.25-mL Fluzone Quadrivalent vaccine.

$P_{0.5\text{mL}}$  = percentage of subjects with fever reaction (temperature  $\geq 100.4^{\circ}\text{F}$  [ $38.0^{\circ}\text{C}$ ]) after vaccination with the first dose and/or the second dose of 0.5-mL Fluzone Quadrivalent vaccine.

### 5.1.1.2 Statistical Methods

The 0.5-mL dose of Fluzone Quadrivalent vaccine will be demonstrated as non-inferior to the 0.25-mL dose of Fluzone Quadrivalent vaccine in terms of fever reaction through an assessment of the rates of any fever (temperature  $\geq 100.4^{\circ}\text{F}$  [ $38.0^{\circ}\text{C}$ ]) during the day of vaccination or during the 7 days following any dose (Dose 1 and Dose 2 combined).

Non-inferiority will be demonstrated if the upper bound of the 2-sided 95% CI of the rate difference between Group 2 (subjects receiving 0.5 mL of vaccine) and Group 1 (subjects receiving 0.25 mL of vaccine) is  $< 5\%$ . The 95% CI of the difference in proportions  $P_{0.5\text{mL}} - P_{0.25\text{mL}}$  will be computed using the Wilson Score method without continuity correction as quoted by Newcombe (3).

To test this hypothesis, a 2-sided 95% CI will be constructed around the difference,  $P_{0.5\text{mL}} - P_{0.25\text{mL}}$ , where  $P_{0.25\text{mL}}$  and  $P_{0.5\text{mL}}$  are the proportions of subjects in Group 1 and Group 2, respectively, experiencing any fever (temperature  $\geq 100.4^{\circ}\text{F}$  [ $38.0^{\circ}\text{C}$ ]) during the day of vaccination or during the 7 days following any dose (Dose 1 and Dose 2 combined).

The hypothesis will be supported by the data, if the upper bound of the calculated 95% CI is  $< 5\%$ . This is the equivalent to testing the null hypothesis using a 1-sided type I error rate of 0.025.

$$H_0: P_{0.5\text{mL}} - P_{0.25\text{mL}} \geq 5\%$$

$$H_A: P_{0.5\text{mL}} - P_{0.25\text{mL}} < 5\%$$

If the null hypothesis is rejected, then the alternative hypothesis of non-inferiority will be supported.

Because of concerns regarding the integrity of safety data collected at Site 009, an additional statistical analysis will be conducted that excludes temperature data collected at this site. The results of this analysis will be reported in the CSR appendices.

Nevertheless, the study conclusion (non-inferiority with respect to the proportion of subjects with fever in Group 1 vs Group 2) will be based on the primary analysis that includes data from Site 009.

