5.1.5 Planned Trial Calendar

The following dates are approximate. The actual dates may differ as, for example, the trial will not start until all the appropriate regulatory and ethical approvals have been obtained.

Planned trial period - FVFS (first visit, first subject) to LVLS (last visit, last subject):
September 2016 to February 2017

Planned end of trial: February 2017

Planned date of final clinical study report: within approximately 10 months of study completion.

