#### 4.3.1.3 Safety Assessment Methods

See Section 9.3.1.3 of the protocol version 2.0, 13 June 2016.

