## 5.7 Changes in the Conduct of the Trial or Planned Analyses

Not applicable.

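### Does the SAP's handling of Site 009, with no entry under planned changes, leave the fever conclusion unsettled?

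*SAP*

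**What the plan says.** SAP 5.1.1.2 sets the primary test: the upper limit of the two-sided 95% interval for the fever difference (0.5 mL minus 0.25 mL) must lie below 5 percentage points. It then adds: "Because of concerns regarding the integrity of safety data collected at Site 009, an additional statistical analysis will be conducted" without that site's temperatures. On reporting it says: "The results of this analysis will be reported in the CSR appendices". The last paragraph states that the conclusion nevertheless "will be based on the primary analysis that includes data from Site 009". SAP 5.1.3.1 adds safety overviews and tables of solicited reactions by maximum intensity without the site, also for the appendices.

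SAP 5.7, headed "Changes in the Conduct of the Trial or Planned Analyses", reads "Not applicable".

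The readable protocol does not mention Site 009. SAP 4.3.1.3 dates the protocol it relies on: "See Section 9.3.1.3 of the protocol version 2.0, 13 June 2016". Protocol 5.1.5 plans first to last visit for "September 2016 to February 2017". On the size of the site, SAP section 5 promises this: "The distribution of the subjects enrolled into the study will be summarized by investigative site and enrollment group".

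**The concern.** The SAP appears to contradict itself. The extra analyses respond to data collected in the trial. The cited protocol is dated before the first planned visit, so it cannot have foreseen them. That makes them an addition to the planned analyses, yet the section for such additions says there are none.

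Two further points seem to follow. The SAP does not describe the problem at the site or give a site-specific reason for keeping it. It also does not say how the fever conclusion would be worded if the bound were met with the site and missed without it.

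The design gives this some weight. In a non-inferiority test of a harm, records that carry no dose signal pull the difference toward zero and so favour success. A reader who does not know the nature of the concern cannot judge whether that applies here.

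**Working it through.** **1. What is disclosed, and where.**

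- Type of concern: integrity of safety data (SAP 5.1.1.2).
- Extra analyses: fever without the site (5.1.1.2) and the main safety tables without it (5.1.3.1).
- Place of reporting: the study report's appendices (both sections).
- Deciding analysis: the one with the site (5.1.1.2).
- General rule that keeps the site: the Safety Analysis Set is fixed for the primary test (Protocol 12.1.1.2, SAP 5.1.1), it contains those who received study vaccine (Protocol 12.2.1, SAP 5.2.1), and all recorded safety data are analysed (Protocol 12.3.1, SAP 5.3.1).
- Missing: an entry in 5.7, the nature of the concern, a site-specific reason for keeping the site, and wording for a disagreement.

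The missing items concern documentation. None leaves the formal test undefined.

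**2. The plan's own figure.** SAP 5.1.1.2 equates the 95% interval with a one-sided error of 0.025. The normal quantile at 0.975 is 1.960, so this reproduces. The sample-size sections are blacked out, so the assumed fever rate is not available and a range is used below.

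**3. How far one site can move the bound.** The interval is Newcombe's, built from Wilson limits (l, u) for each arm. With p₂ for 0.5 mL and p₁ for 0.25 mL:

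upper limit = (p₂ − p₁) + √[(u₂ − p₂)² + (p₁ − l₁)²]

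Inputs: 1095 per arm (Protocol 5.1.3) and about 38 centers (Protocol section 3). An average site has 2190/38 = 57.6 subjects, or about 29 per arm. Assumed: a 10% fever rate in the 0.25-mL arm, and no fever recorded at the site in either arm.

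- With the site, the largest passing result is 135/1095 against 110/1095. The difference is 12.329 − 10.046 = 2.283 points, u₂ = 14.409 and l₁ = 8.403. Upper limit = 2.283 + √(2.080² + 1.643²) = 4.93.
- Without the site, 135/1066 against 110/1066. The difference is 2.345, u₂ = 14.796 and l₁ = 8.633. Upper limit = 2.345 + √(2.131² + 1.686²) = 5.06.
- One case fewer without the site, 134/1066, gives 4.96, which passes. The verdict therefore turns on the site for a single count: observed differences above 2.19 (24/1095) and up to 2.28 points (25/1095).

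With assumed rates of 5%, 10%, 15% and 20%, the just-passing upper limits of 4.92, 4.93, 4.99 and 4.95 become 5.05, 5.06, 5.11 and 5.07 when 29 per arm without fever are removed. If the site has the same rates as the rest, the bound moves by only 0.03 to 0.04 points.

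**4. The same question with some loss of subjects.** Assumed: 1040 evaluable per arm (1095 × 0.95), and 0.25-mL fever rates of 8%, 15% or 20%. The table gives the largest 0.5-mL fever count at the other sites that meets the bound, with the 0.25-mL arm at its expected count.

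| Site share | Fever rate | Site left out | Site added, equal rates | Site added, no fever |
|---|---|---|---|---|
| 1/38 (27 per arm; 1013 elsewhere) | 8% | 105 | 106 | 107 |
| | 15% | 170 | 171 | 171 |
| | 20% | 217 | 218 | 219 |
| 10%, assumed (104 per arm; 936 elsewhere) | 8% | 97 | 100 | 101 |
| | 15% | 155 | 159 | 160 |
| | 20% | 199 | 202 | 204 |

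The window is 1 to 2 cases at 1/38 (about 0.1 to 0.2 points) and 3 to 5 cases at 10% (0.3 to 0.5 points).

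**5. How often the two analyses would disagree by chance.** These rates come from 1,000,000 simulated trials per setting, with sound data at every site. The bound is met with the site and missed without it in 0.4–2.3% of trials at no true difference and in 2.9–3.1% at a true 2-point difference (share 1/38). At a 10% share the figures are 1.1–6.1% and 6.7–7.5%. A separate run of 500,000 trials per setting gave the reverse pattern at 1/38 in 0.15–1.3% and 1.8–2.1%. A disagreement is therefore not in itself evidence of bad data.

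**The case for a change.** The strongest case for acting is that the contradiction in 5.7 is real and cheap to remove, and that wording for a contrary result is best fixed before results are known. If the site's records carry no dose signal, the type I error rises from 2.5% to 2.9–3.1% at a 1/38 share and to 4.5–5.7% at an assumed 10% share. A reader would want to know whether that applies.

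The point about 5.7 stands. The analyses are additions and the entry does not list them. Anyone reading the primary test still meets them at once, with their reason.

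The error rates stand as arithmetic under their assumptions. They measure the effect of keeping the site in the test, which the protocol's analysis set requires and which better documentation would not alter. The planned analysis without the site is the tool for judging that effect.

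The rest is weaker. The SAP names the appendices as the place of reporting, but it does not bar discussion in the body of the report, and its table shells are in a separate file (SAP section 6). A label that the result is sensitive to the site would often mark noise, and it would need a counterpart for the reverse pattern. Details of the problem may also stand in text that is not visible, since parts of the SAP Introduction are blacked out and front pages were removed. SAP 5.1.1.2 and 5.7 themselves show no redaction.

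**Conclusion.** No change to the plan follows. The one inconsistency is a clerical omission in SAP 5.7, because the additions are disclosed where they matter. The missing account of the site's problem is detail that the study report can supply. Placing the result in the body or the appendices, and wording a disagreement, are reporting choices. The rule for the formal conclusion is already set, and it rests on the analysis with the site.

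The verdict depends on the site only when the upper limit is already close to 5%: within 1 to 2 fever cases at a 1/38 share, or 3 to 5 at an assumed 10% share. This rests on assumed fever rates of 5% to 20% in step 3 and 8% to 20% in step 4, an assumed 5% loss in step 4, and an assumed size for Site 009. The planned summary by site and group will show the actual size. The success criterion, type I error and power are the same whether or not 5.7 is filled in.
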